14. DATA QUALITY ASSURANCE

To ensure accurate, complete, and reliable data, the sponsor or its representatives will do the following:

- Provide instructional material to the study sites, as appropriate.
- Perform start-up training to instruct the Investigators and study personnel. This training will give instruction on the protocol, the completion of the eCRFs, and study procedures.
- Make periodic visits to the study site.
- Be available for consultation and stay in contact with the study site personnel by email, telephone, or facsimile.
- Review and evaluate eCRF data and use standard computer edits to detect errors in data collection.
- Conduct a quality review of the database.

Authorized representatives of the sponsor, a regulatory authority, or an IRB/IEC may visit the site to perform audits or inspections, including source data verification. The purpose of an Alexion audit or inspection is to systematically and independently examine all study-related activities and documents to determine whether these activities were conducted, and data were recorded, analyzed, and accurately reported according to the protocol, good clinical practice (GCP) guidelines of the International Conference on Harmonisation (ICH), and any applicable regulatory requirements. The Investigator should contact the sponsor immediately if contacted by a regulatory agency about an inspection.

To ensure the safety of participants in the study, and to ensure accurate, complete, and reliable data, the Investigator will keep records of laboratory tests, clinical notes, and patient medical records in the patient files as original source documents for the study. If requested, the Investigator will provide the sponsor, applicable regulatory agencies, and applicable IRBs/IECs with direct access to original source documents.

14.1. Data Collection and Storage

All clinical data will be recorded promptly and accurately in the EDC system. When recorded electronically, CRFs will be electronically generated. All raw data will be preserved in order to maintain data integrity. The Investigator or designee will assume the responsibility of ensuring the completeness, accuracy, and timeliness of the clinical data.

The EDC system is fully validated and compliant with CFR Title 21 Part 11. The EDC system will maintain a complete audit trail of all data changes. At each scheduled monitoring visit, the Investigator or designee will cooperate with the sponsor's representative(s) for the periodic review of study documents to ensure the accuracy and completeness of the EDC system.

Electronic consistency checks and manual review will be used to identify any errors or inconsistencies in the data. This information will be provided to the respective study sites by means of electronic or manual queries.

The Investigator or designee will prepare and maintain adequate and accurate source documents (medical records, ECGs, AE and concomitant medication reporting, raw data collection forms) designed to record all observations and other pertinent data for each patient receiving study drug.

The Investigator will allow the sponsor's representatives, contract designees, authorized regulatory authority inspectors, and the IRB/IEC to have direct access to all documents pertaining to the study.

14.2. Records Retention

The Investigator must maintain all documentation relating to the study for a period of 2 years after the last marketing application approval, or if not approved, 2 years following the discontinuance of the test article for investigation or longer if required per local regulations. If it becomes necessary for the sponsor or the sponsor's designee or the Regulatory Authority to review any documentation relating to the study, the Investigator must permit access to such records.

15. STATISTICAL METHODS AND PLANNED ANALYSES

15.1. General Considerations

All data collected will be presented in summary tables and tabulations. All data, as well as any outcomes derived from the data, will be presented in detailed data listings. Graphical displays may also be provided, when appropriate. All analyses will be performed using SAS[®] release, version 9.4 or higher (SAS Institute Inc., Cary, NC, USA) or other validated statistical software. Continuous variables will be summarized using descriptive statistics, including number of observations and mean, standard deviation (SD), median, minimum, and maximum values. Categorical variables will be summarized by frequency counts and percentage of patients. Prior to finalizing and locking the database, all decisions concerning the inclusion or exclusion of data from the analysis for each patient will be determined by appropriate medical and statistical personnel. Any and all exclusions will be documented in patient listings.

Details of the statistical analyses described below will be specified in a separate Statistical Analysis Plan (SAP) before database lock and analysis. Any change to the data analysis methods described in the protocol will require an amendment only if it changes the primary or key secondary objectives or the study conduct. Any other change to the data analysis methods described in the protocol or SAP, and the justification for making the change, will be described in the clinical study report (CSR). Additional exploratory analyses of the data may be conducted as deemed appropriate.

An interim CSR will be prepared at the end of the 26-week Initial Evaluation Period, which will include efficacy, safety, and PK/PD analyses. A final CSR to summarize long-term efficacy, safety, and PK/PD will be produced at study completion. Available exploratory data will be summarized after study completion but may not be included in the CSR.

For patients who discontinue ALXN1210 treatment, but remain in study, their data will be summarized along with data from patients remaining on treatment for 8 weeks (56 days) after their last dose of study drug. Data beyond this point will be presented in separate supplemental listings strictly limited to these patients. If such patients start retreatment with ALXN1210, their data from the time of study treatment restart will also be presented in separate supplemental listings limited to patients who will have restarted study treatment. However, data on AE, concomitant medications, and nonpharmacologic therapies and procedures from the time of treatment restart will be considered treatment emergent or concomitant, and will be summarized as such, combined with data from patients who remained on treatment throughout the study.

Pharmacokinetic/PD and ADA data from patients who discontinue ALXN1210 treatment, but remain in study, will be summarized along with data from patients remaining on treatment, until 8 weeks after their last dose of study drug. Data beyond this point will be presented in separate supplemental listings limited to these patients. If such patients start retreatment with ALXN1210, their PK/PD and ADA data from the time of study treatment restart will also be presented in separate supplemental listings limited to patients who will have restarted study treatment.

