6.2.4. Safety Endpoints

The safety and tolerability of ALXN1210 will be evaluated by physical examinations, vital signs, electrocardiograms (ECGs), laboratory assessments, and incidence of AEs and SAEs. The proportion of patients who develop antidrug antibodies (ADA) will also be assessed.

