- ^l A predose serum sample will be collected on Days 351, 575, 743, and Day 911. For patients who discontinue treatment but remain in the study, ADA sample will be collected at any time during the visits until approximately 39 weeks after the last dose of ALXN1210. In case of retreatment, if the patient starts the retreatment on a scheduled visit which does not include ADA sample collection, a predose ADA sample must be collected. If a supplemental dose is administered, a predose ADA sample will be collected. All collection times will be recorded in the eCRF.
- ^m Review the Clinical Trial Participant Safety Information Card with the patient and discuss the importance of carrying the safety card at all times, and the risks ALXN1210 treatment, including the risk of meningococcal infection.
- ⁿ Concomitant medications must be collected at all study visits (and at the 56 [± 5]-day follow-up phone call for patients who terminate the study early) and checked against the prohibited medication listed in [Section 9.7](#).
- ^o Extension Period begins at the start of Day 183 dosing. The dose of ALXN1210 is based on the patient's body weight recorded at the last visit or more recently. For patients who discontinue ALXN1210 treatment, remain in the study, and further receive retreatment, the dosing details are provided in [Section 8.3.2.1](#).

Table 3: Schedule of Study Visits and Assessments: Extension Period Day 967 to Day 1863

Period	Extension Period																
	967	1023	1079	1135	1191	1247	1303	1359	1415	1471	1527	1583	1639	1695	1751	1807	1863/ ET/EOS
Study Day	±7	±7	±7	±7	±7	±7	±7	±7	±7	±7	±7	±7	±7	±7	±7	±7	±7
Window (day)	±7	±7	±7	±7	±7	±7	±7	±7	±7	±7	±7	±7	±7	±7	±7	±7	±7
Weight	X	X	X	X	X	X	X	X	X	X	X	X	X	X	X	X	X
Pregnancy test ^a	X	X	X	X	X	X	X	X	X	X	X	X	X	X	X	X	X
FACIT-Fatigue questionnaire /Pediatric FACIT-Fatigue questionnaire ^{b,c}				X				X				X				X	X
EQ-5D-3L questionnaire ^c				X				X				X				X	X
Physical examination																	X
Abbreviated physical examination ^d	X	X	X	X	X	X	X	X	X	X	X	X	X	X	X	X	X
Assessment of extra-renal signs or symptoms of aHUS				X				X				X				X	X
Vital signs ^e	X	X	X	X	X	X	X	X	X	X	X	X	X	X	X	X	X
Safety 12-Lead ECG ^f																	X
Chemistry	X	X	X	X	X	X	X	X	X	X	X	X	X	X	X	X	X
LDH isozymes ^g	X	X	X	X	X	X	X	X	X	X	X	X	X	X	X	X	X
Hematology and coagulation ^h	X	X	X	X	X	X	X	X	X	X	X	X	X	X	X	X	X
Urinalysis and urine chemistry	X	X	X	X	X	X	X	X	X	X	X	X	X	X	X	X	X
PK/PD sampling ⁱ			X ⁱ			X ⁱ			X ⁱ				X ⁱ			X ⁱ	X ⁱ

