15.9.5. Immunogenicity

Abnormal immunogenicity findings, including the incidence and titers for ADAs to ALXN1210 will be presented at each postbaseline time point in tabular format. The proportion of patients ever positive and the proportion of patients always negative may be explored.

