7.2.1.2. Subgroup Analysis

The primary efficacy analysis will be repeated separately by the following subgroups:

- gender (male, female)
- race
- ethnicity
- geographic region (by country)
- age at enrollment categories (12-17, 18 years of age and up)
- kidney transplant history (yes, no)
- immunogenicity status (ever positive, always negative)
- dialysis within 5 days prior to treatment initiation (yes, no)
- met all laboratory criteria for TMA as determined by the central laboratory at Day 1

Given that the number of patients in these subgroups may be limited, the CIs will be based on exact confidence limits using the Clopper-Pearson method. For the same reason, some subgroup categories may be combined.

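### For patients who stop drug but stay in the study, the 8-week and retreatment listing rule could keep late first ADA positives out of the cumulative ADA proportion, because no window is set for ever positive/always negative

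*Protocol*

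**What the plan says.** The rule is in Protocol section 15.1 and applies only to patients who discontinue ALXN1210 and remain in the study. For them, "Pharmacokinetic/PD and ADA data from patients who discontinue ALXN1210 treatment, but remain in study, will be summarized along with data from patients remaining" and, continuing, "on treatment, until 8 weeks after their last dose of study drug". After that, "Data beyond this point will be presented in separate supplemental listings limited to these patients". If such a patient is retreated, "their PK/PD and ADA data from the time of study treatment restart will also be presented in separate supplemental listings". The paragraph just before treats other data differently: adverse events, concomitant medications and procedures after restart count as treatment emergent or concomitant and are summarized together with the patients who never stopped.

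Sampling runs well past the cut. Table 2, footnote l (section 7.3) says that after discontinuation an "ADA sample will be collected at any time during the visits until approximately 39 weeks after the last dose of ALXN1210". Table 3, footnote m and section 8.3.2 say much the same. Section 8.3.2.1 adds predose ADA samples at the retreatment start and at the supplemental doses.

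The endpoint in section 6.2.4 is cumulative and has no time limit: "The proportion of patients who develop antidrug antibodies (ADA) will also be assessed". SAP section 5.2 repeats it. On patient status, Protocol section 15.9.5 says "The proportion of patients ever positive and the proportion of patients always negative may be explored". SAP section 7.3.3.3.2 makes that summary firm, again with no window. SAP section 7.2.1.2 also uses the status as a subgroup factor for the primary endpoint: "immunogenicity status (ever positive, always negative".

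**The concern.** Whether a patient has ever developed ADA is a property of the whole record. A cut tied to time since last dose suits by-visit tables, where a patient beyond the cut can leave both numerator and denominator. It does not suit a cumulative proportion, where the patient stays in the denominator and a late positive is lost from the numerator.

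The patients affected are of particular interest for immunogenicity. Some will have stopped after the serious infusion or serum sickness-like reactions listed in section 8.3.2, and some will be re-exposed after a gap. After re-exposure, a reaction enters the main adverse event tables while the ADA result that might help explain it appears only in a listing.

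**Working it through.** The documents give no ADA rate, no expected number of discontinuations and no expected number of late seroconversions, so there is no planned figure to reproduce. Two things can be checked: where the scheduled samples fall relative to the cut, and how far one reclassified patient moves the result.

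**Inputs**
- Counted window: days 1 to 56 after the last dose (section 15.1).
- Listing-only window: days 57 to 273, taking about 39 weeks as 39 × 7 = 273 days.
- ADA days (Tables 1 to 3): 71, 127, 183, 351, 575, 743, 911, 1079, 1247, 1415, 1639, 1807 and 1863.
- Possible extension last-dose days: 183 + 56k for k = 0 to 29, that is Day 183 to Day 1807, 30 days given equal weight.
- Planned enrolment: about 55.

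**Sample count, extension**

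For each last-dose day d, count ADA days in (d, d + 56] and in (d + 56, d + 273].

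| | Result |
|---|---|
| Last-dose days with a sample within 56 days | 10 of 30 (Days 295, 519, 687, 855, 1023, 1191, 1359, 1583, 1751, 1807) |
| Last-dose days with none within 56 days | 20 of 30; all 20 have a sample by day 273 |
| Scheduled samples in the counted window | 10, each at nominal day 56 |
| Scheduled samples in the listing-only window | 29 |

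Examples: a last dose on Day 183 has its next ADA sample on Day 351 (351 − 183 = 168 days). A last dose on Day 351 has its next on Day 575 (224 days). Listing-only samples are 29/(10 + 29) = 74% of the total. All 10 countable samples sit on the edge of the window, and extension visits have a ±7-day allowance, so one taken late falls outside.

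Footnotes l and m could instead be read as sampling at every visit after stopping. The nominal days would then be 56, 112, 168 and 224: one counted and three not.

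**Initial Evaluation Period**

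Last doses on Days 15, 71 and 127 each have an ADA sample at exactly 56 days (Days 71, 127 and 183). A patient given only the Day 1 dose has the first sample on Day 71, 70 days later, and so has no countable postbaseline result.

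**Effect per patient**

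One patient in 55 is 1/55 = 1.8 percentage points. Suppose no patient is positive in the counted data (Clopper-Pearson limits):

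| Late first positives (assumed) | Proportion if counted | 95% CI |
|---|---|---|
| 0 | 0% | 0 to 6.5% |
| 1 | 1.8% | 0.05 to 9.7% |
| 2 | 3.6% | 0.4 to 12.5% |
| 3 | 5.5% | 1.1 to 15.1% |

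If the rule governs the cumulative proportion, every row is reported as 0%.

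**The case against.** A reader might infer that the plan labels late positives as always negative and that ADA incidence is therefore understated. The documents do not go that far. No text assigns that label. Neither section 15.9.5 nor SAP section 7.3.3.3.2 sets a window, and the SAP contains neither the 8-week nor the retreatment rule, so a programmer working from the SAP could use every result. SAP section 4.1 reports no changes from the protocol, but that settles little: the SAP still describes an Extension Period of up to 2 years and seems to predate the current protocol. Bias also needs at least one late first positive, and there may be none. The sample counts describe opportunity over hypothetical stopping days, not misclassified patients. All of this stands.

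The 8-week cut is also a coherent choice for the off-drug period. It matches section 15.9.1, where events starting 56 days or later after the last dose are not treatment emergent. That defence does not cover the period after retreatment, where adverse events are pooled and ADA results are not. The listings do let a reader match a reaction to a patient's ADA result, but they do not repair a summary proportion.

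A reader might also infer a distorted subgroup of the primary analysis. The documents give little support for this. The endpoint covers 26 weeks and the retreatment instructions refer only to the Extension tables. Within 26 weeks, only a last dose on Day 1, 15 or 71 leaves any ADA sample beyond the cut. Nor does anything say that a patient with no countable sample would be called always negative.

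Finally, retreatment does not bring an ADA sample at every dose. The extra predose samples are specified for the retreatment start and supplemental doses; later visits return to the regular schedule.

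**Conclusion.** The point holds as a conditional one. Section 15.1 names ADA data explicitly, so this is more than a missing detail: applied as written, it removes late first positives from the summarized data, while the endpoint asks who develops ADA at any time. Under that reading, cumulative incidence could be too low and the always-negative proportion too high. Under the other reading the status is undefined and the choice is left to programming. Either way the text needs settling.

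The size cannot be estimated from the documents. It is zero with no late first positives and about 1.8 percentage points for each one, assuming a denominator of about 55. One such patient would separate a report of no ADA from a report of some. The issue is confined to patients who stop drug but stay in the study. By-visit percentages need not be affected, and the effect on the 26-week subgroup is minimal. This is a correction worth making to a descriptive safety summary; it does not threaten the primary analysis.

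**What to change.** Keep the 8-week cut for the by-visit ADA tables. In Protocol sections 15.1 and 15.9.5 and SAP section 7.3.3.3.2, state that the proportion developing ADA, and ever positive/always negative status, use all postbaseline ADA results, including off-treatment samples to about 39 weeks and samples after retreatment. Show patients with no postbaseline ADA result as not evaluable rather than negative.

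The cost is a sentence or two in each place and a small programming change. No new samples are needed. The reported ADA incidence may rise slightly.

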15.2. Determination of Sample Size

Approximately 55 patients will be enrolled in this study in order to yield at least 50 evaluable patients by Day 183. This sample size is deemed appropriate to provide complete safety information and the necessary precision level for the planned estimation. Assuming a proportion of Complete TMA response of 65%, 50 patients would yield a 95% confidence interval (CI) for the proportion of response with a half-width of approximately 15%.

The sample size was increased to 55 patients to account for a potential 10% drop-out rate, thus yielding a total planned sample size of 55 patients.

15.3. Analysis Sets

Efficacy analyses will be performed on the FAS. The analysis of the FAS will be the primary analysis.

The FAS will be based on a mITT approach where patients that were enrolled and treated based on verification of inclusion and exclusion criteria through local laboratory results and the assumption that all inclusion and exclusion criteria were satisfied will be excluded from the FAS if it is later shown that certain of the inclusion and exclusion criteria were in fact not satisfied once all Screening laboratory results are available. Based on the above, the FAS will include all patients who receive at least 1 dose of ALXN1210, have at least 1 postbaseline efficacy assessment, and meet all of the following criteria:

- Patients who satisfy Inclusion Criterion number 2c
- Patients who satisfy Exclusion Criterion number 1
- Patients who satisfy Exclusion Criterion number 2

The FAS will be determined prior to database lock and prior to the database snapshot for the analysis performed at the end of the 26-week Initial Evaluation Period.

Safety analyses will be performed on the Safety Set, defined for all patients who receive at least 1 dose of study drug.

Pharmacokinetic and PD analyses will be performed on all patients who receive at least 1 dose of study drug and who have evaluable PK and PD data.

15.4. Demographics and Baseline Characteristics

Patient demographic and baseline characteristics, including medical history and transplant history, will be summarized for the FAS and Safety Set.

15.5. Patient Disposition

All patients will be included in the summaries of patient disposition, which will describe the frequency and percentage of patients enrolled and treated and who completed or withdrew from the study, along with reason for withdrawal from the study.

The numbers of patients who are treated, discontinue treatment (along with reason for treatment discontinuation), complete or withdraw from the Initial Evaluation Period (along with reason for

withdrawal), enter the Extension Period, and complete or withdraw from the Extension Period (along with reason for withdrawal) will be tabulated.

15.6. Prior and Concomitant Medications and Nonpharmacologic Therapies and Procedures

Each patient's prior and concomitant medication use will be coded using the World Health Organization Drug Dictionary, and the frequency and percentage of concomitant medications will be summarized. Medications will be summarized by Anatomic-Therapeutic-Chemical (ATC) class and preferred drug name using frequency counts and percentages of patients in the Safety Set.

15.7. Treatment Compliance

The number of infusions received per patient will be tabulated for the FAS and Safety Set.

15.8. Efficacy Analyses

All efficacy analyses will be conducted for the FAS. The FAS is the primary analysis set for all efficacy analyses.

15.8.1. Primary Efficacy Analysis

The primary efficacy endpoint is Complete TMA Response during the 26-week Initial Evaluation Period. The primary analysis will consist in estimating the proportion of complete TMA responders among ALXN1210 treated patients. This will be performed by calculating the point estimate and a 95% CI for the proportion of complete TMA responders in ALXN1210 treated patients. The CI will be based on the asymptotic Gaussian approximation method with a continuity correction.

15.8.2. Key Secondary Efficacy Analyses

15.8.2.1. Dialysis Requirement Status

For patients requiring dialysis within 5 days prior to ALXN1210 treatment initiation, the proportion of patients no longer requiring dialysis will be summarized over time. A 2-sided 95% CI for the proportion receiving dialysis will be provided.

